### **Background, Rationale and Context**

One lung ventilation (OLV) is commonly used in thoracic surgery to improve surgical exposure and improve operative conditions. At this time, there are two approaches to OLV in routine use in adult thoracic surgery. One approach is to use of a double lumen tube (DLT). The other approach is to use a bronchial blocker (BB). Currently there are several different types of bronchial BBs on the market.

The EZ-Blocker is a bronchial blocker with a 7-Fr shaft with two separate occlusive balloons “Y” configuration designed to rest on the carina. Once secured in place, the operator can choose to inflate one of the two occlusive balloons to isolate either mainstem bronchus (1).

Studies have been performed comparing BBs to DLTs looking at time and ease of placement, differences in quality of lung isolation, and incidence of sore throat, hoarseness, and other morbidity associated with placement [2-4]. A recent meta-analysis published by Clayton-Smith et al found that BBs are associated with fewer airway injuries when compared to DLTs (5). They found the quality of isolation to be equivalent between BBs and DLTs. While quality of isolation over all may be comparable, it has been demonstrated in several studies that positional stability of bronchial blockers such as the Arndt or Cohen, is frequently inferior to that of a DLT (2,4).

At this time, there are a small number of trials looking at the use of the EZ-blocker in adult patients. In one study published in 2013 the EZ-blocker was compared to the Cohen Flex-Tip blocker. In this study they found that time to place the EZ-blocker was in fact shorter and that overall the number of repositioning required was less with the EZ-blocker (6). In 2013, a study was published by Mourisse et al which compared DLT to the EZ-blocker (7). In this study they found initial malposition of both devices to be fairly equivalent, and time to placement was longer with the EZ-blocker. They also found more tracheal and bronchial injuries in the DLT group, but importantly they found that positional stability was equivalent. In both of these studies however they did not design their studies to effectively differentiate between right and left sided procedures when quantifying the need for BB repositioning. Because the take off of the right upper lobe bronchus is sometimes adjacent to, or even proximal to the carina, it can impede effective isolation with a BB. Therefore, claims of positional stability may rely heavily on the laterality of the procedure, with right sided isolation being significantly more labile than left sided especially with respect to isolation using a BB.

In conclusion then, we feel that the potential morbidity of a DLT in terms of the potential for airway injury when compared to a BB suggests that further exploration of the possibility of equivalent positional

stability between these devices is necessary. We feel it is necessary to delineate the impact of laterality on the effectiveness of one technique for isolation versus the other.

In addition to this if there is a difference in stability in cases where right sided isolation via the EZ-blocker fails in the setting of multiple repositions or out and out failure we would like to examine the preoperative CT data to determine if there are anatomic measurement which could potentially inform the appropriateness or inappropriateness of choosing a DLT over an EZ-blocker.

## **Objectives**

The objective of this study is to evaluate the positional stability and quality of lung isolation provided by the EZ-blocker compared to a DLT for both right and left sided thoracic surgery.

An additional objective will be to assess time to placement of both devices and other significant clinical differences between these two approaches to placement of the BB including airway injury and post-operatives sore throat, post-operative hoarseness, Additionally we would like to examine the preoperative high resolution CT imaging data to determine if there are anatomic landmarks that may potentially inform the appropriateness or inappropriateness of choosing an EZ-blocker or left sided DLT.

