## **Methods and Measures**

### **Design**

Once the patient is recruited preoperatively in the PAC or within the hospital as an inpatient, this information will be relayed to the study investigators. On the day of surgery, the patient will then be randomized using a random number generator and opaque envelope method for group allocation to either extra-luminal placement of an EZ blocker bronchial blocker or left side double lumen tube. We will recruit at least 80 patients with right sided procedures: 40 EZ-Blocker and 40 left sided DLT. We will also recruit at least 80 patients with left sided procedures: 40 EZ-Blocker and 40 left sided DLT.

We will record age, height, weight, gender, ASA status, type of surgery, side of surgery, duration of one lung ventilation, duration of surgery, and duration of anesthesia.

An IV will be placed in the patient prior to going to the OR. Once in the OR the patient will have routine monitors placed. The patient will be pre-oxygenated with 100% O2 for 2 minutes and induced.. The patient will then be hand ventilated with 100% oxygen for 3 minutes to ensure relaxation. Patients will undergo direct laryngoscopy and according to group assignment will have either an extraluminal EZ-blocker placed or an appropriately sized left sided double lumen placed under the supervision of an attending experienced in thoracic anesthesia and one lung ventilation.

We will confirm endotracheal placement of the ETT or left sided DLT via auscultation and ETCO2. The ETT or DLT will be secured at an appropriated depth. The fiberscope will then be advanced into the lumen of the ETT or DLT to further adjust and confirm placement of the EZ-blocker or DLT. Time for initial bronchial blocker placement or DLT placement will be recorded from the point of the DL to removal of the fiberscope after visualization of the BB with the cuff inflated in the correct position or the DLT with the bronchial cuff inflated.

Other intravascular lines such as a radial arterial line and additional peripheral IV may be placed at the discretion of the attending anesthesiologist.

Once in the final position prior to prepping and draping the blocker or DLT in all groups will be checked to make sure it is still correctly placed with a FOB. The patient will be prepped and draped.

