### **Outcome Measure(s)**

We will measure the number of DLT or BB replacements, time of placement, quality of isolation at 1-hour intervals during the operation, incidence of sore throat and/or hoarseness postoperatively.

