## Appendix 1 Data Sheet

### Data Form for EZ-bronchial Blocker vs. Double Lumen Study

Patient Sticker

ASA:

Weight:      Height:      BMI:

Gender:

Diagnosis:

Laterality:      RIGHT      LEFT

EZ-Blocker      DOUBLE LUMEN

Induction Drug Doses:

Propofol \_\_\_\_\_      Fentanyl \_\_\_\_\_      Rocuronium(0.8mg/kg) \_\_\_\_\_  
Etomidate \_\_\_\_\_

Ventilate/Wait 3 minutes at least.

Begin Blocker or Double Lumen with DL. START TIMING:

Time for placement of EZ-blocker or DLT: \_\_\_\_\_

Number of EZ-blocker or DLT Replacements During Procedure: \_\_\_\_\_

Quality of Isolation: 1- Excellent      2 – Fair      3 - Poor

Time 1 \_\_\_\_\_      Quality of Isolation T1 \_\_\_\_\_

Time 60 min      Quality of Isolation 60 \_\_\_\_\_

Time 120 min      Quality of Isolation 120 \_\_\_\_\_

Time 180 min      Quality of Isolation 180 \_\_\_\_\_

Time 240 min      Quality of Isolation 240 \_\_\_\_\_

Time 300 min      Quality of Isolation 300 \_\_\_\_\_

(Excellent=complete collapse with perfect surgical exposure; Fair=total collapse but the lung has residual air; Poor=no collapse, or partial collapse with interference in surgical exposure)

Incision Time: \_\_\_\_\_      Closure Time: \_\_\_\_\_      Time of OLV \_\_\_\_\_

Sore Throat Post procedure:  
VAS score from page 3

Day 1 \_\_\_\_\_

Day 2 \_\_\_\_\_

Additional Comments/Adverse Events/Other significant intra-operative events

Blocker or Double Lumen Replacement

Replacement Event:	Time	Brief Description of event including duration of replacement event
		Too Deep Too Proximal Other

## Day 1

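### Airway injury is named in an additional objective, but no outcome, directed examination or form item measures it, so the devices cannot be compared systematically on it

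*Combined protocol and SAP*

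**What the plan says.** The main objective, in the Objectives section of the combined protocol and SAP, is positional stability and quality of lung isolation, for right- and left-sided surgery. An additional objective covers placement time and "other significant clinical differences between these two approaches to placement of the BB including airway injury and post-operatives sore throat, post-operative hoarseness". Injury is listed beside sore throat and hoarseness, as a separate item.

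Background, Rationale and Context explains the interest. It cites a meta-analysis finding that "BBs are associated with fewer airway injuries when compared to DLTs", and concludes that "the potential morbidity of a DLT in terms of the potential for airway injury when compared to a BB suggests that further exploration" of whether the two devices are equally stable is needed.

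Outcome Measure(s) reads "We will measure the number of DLT or BB replacements, time of placement, quality of isolation at 1-hour intervals during the operation", and ends with "incidence of sore throat and/or hoarseness postoperatively". Airway injury is not there.

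In the Design section the fibrescope has a positional purpose: "The fiberscope will then be advanced into the lumen of the ETT or DLT to further adjust and confirm placement". A second check, before draping, confirms that the device is still correctly placed. Extubation follows usual practice. The Appendix 1 Data Sheet has no injury item; the nearest entry is a line headed "Additional Comments/Adverse Events/Other significant intra-operative events".

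**The concern.** A stated objective needs a defined measure, a time at which someone looks, and a place to write the answer. Airway injury has none of these.

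If the plan is followed as written, the final report either says nothing about a named objective or tabulates whatever staff chose to write down. In such a table a blank has three possible meanings: no injury, nobody looked, or nobody wrote it down. Low counts in both arms could then be taken as a finding that the devices are equally safe. Observations not made at the bedside cannot be recovered later.

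**Working it through.** **1. Trace each item from objective to form.** The CT imaging question is left aside.

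| Item in Objectives | Outcome Measure(s) | Design | Appendix 1 Data Sheet |
|---|---|---|---|
| Positional stability | Number of replacements | Loss of isolation and repositioning, with time and cause | Count, plus event table coded by direction |
| Isolation quality | Hourly | Blinded surgeon asked on entry and every 60 minutes | Three defined grades, up to 300 minutes |
| Placement time | Listed | Start and stop points defined | Field |
| Sore throat | Incidence | VAS 0–100, days 1 and 2 | VAS, both days |
| Hoarseness | Incidence | Asked on days 1 and 2 | No field |
| Airway injury | Not listed | No directed examination | No field |

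Airway injury is the only row that is empty in all three columns. The Analytical Plan names no injury comparison either.

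**2. What the scheduled looks could show.** There are two: one at placement and one before draping. Both are specified for device position. Both come before surgery starts, so neither can show injury that arises during one-lung ventilation, at repositioning or at removal. No observation is tied to removal or exchange of the device.

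**3. Where an overt injury could still be recorded.**
- Design requires significant morbidity and mortality to day 2 to be recorded. Its examples (such as stroke) are illustrative, so a serious airway injury would fit.
- Interventions and Interactions has a study representative ask about post-operative issues on days 1 and 2, with sore throat and hoarseness as examples.
- The data sheet has the adverse-event line quoted above.
- The section on reporting unanticipated problems covers adverse events that are serious and unexpected.

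None of these names airway injury, defines or grades it, or asks about it in every patient. They can pick up an injury that declares itself. They would not reliably pick up a minor or symptomless one.

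**4. Whether the size can be calculated.** The plan's only sizing is in Sample Size: 0.3 against 0.5 repositionings per hour, SD 0.3, 80% power, 5% type 1 error. Taking the test as two-sided:

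n per arm = 2 × (1.960 + 0.842)² × 0.3² / (0.5 − 0.3)² = 2 × 7.85 × 0.09 / 0.04 = 35.3, rounded up to 36.

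This reproduces the stated 36 per arm. Power under the same approximation is 80.7% at 36 and 84.6% at the 40 to be enrolled per device and side. The calculation concerns repositioning only. The documents give no injury rate for either device, so neither power for injury nor the number of injuries missed can be derived from them.

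**5. Which moments would give a fair comparison.** On the plan's own rates, 0.5 / 0.3 = 1.67. For equal operating time, EZ-blocker patients are projected to have about 67% more repositionings. A yes/no item completed at every repositioning would give that arm more chances for an injury to be seen, whatever the true rates. Design also does not say that repositioning uses a fibrescope. The two scheduled checks and removal or exchange of the device apply to every patient in both arms.

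**The case against.** The strongest reply is that this is one item in an additional objective. Background already takes fewer blocker injuries as shown by earlier studies, and uses that only as the motive for asking about stability. On this view the trial need not prove the injury difference again, and overt injury has several routes into the record.

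Most of this stands, and it rules out two stronger readings that a reader might infer:
- **Injury is not recorded anywhere.** The documents do not support this. General morbidity recording, the day 1 and day 2 contact and the adverse-event line are all open to it.
- **The trial fails at its central purpose.** This is not supported either. The main objective and the sample size concern stability and isolation, and the safety argument for blockers is placed on prior evidence.

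The reply does not remove the mismatch. Objectives still promises to assess injury in this trial, separately from the symptoms, and unprompted recording does not deliver that. If the sponsor prefers to rely on earlier evidence, the objective can be deleted.

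It can also be objected that added items would be unblinded and underpowered. Only the surgeon is described as blinded, so recording by those handling the device would be unblinded. No power for injury has been established. Both are reasons for descriptive reporting with stated limits. Neither is a reason to keep an objective that has no measure.

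**Conclusion.** The point holds as a mismatch between a stated additional objective and what the plan collects. Airway injury has no outcome entry, no examination directed at it and no form item. Overt cases may be recorded, but without prompt or definition, so a systematic comparison between the EZ-blocker and the double lumen tube is not possible.

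No numerical size is claimed, because any figure would need injury and capture rates that the documents do not give. The conclusion rests on the text alone and assumes that the data sheet in Appendix 1 is the complete form. It should be corrected before enrolment. It does not affect the comparison of repositioning or isolation quality.

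**What to change.** Add a mandatory coded yes/no item to the data sheet, completed for every patient in both arms at shared moments:
- at each of the two scheduled fibrescope checks: visible bleeding, haematoma or mucosal tear;
- at device removal or exchange: blood on the device or in secretions.

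Record anything seen during repositioning in a separate field and keep it out of the between-arm comparison.

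Add the item to Outcome Measure(s) as a descriptive outcome, clinically evident airway injury, and narrow the wording in Objectives to match. State there or in the Analytical Plan that recording is unblinded, that the trial is not powered for this outcome, and that a low count is not evidence of equal safety.

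If the item is not added, delete airway injury from Objectives.

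The cost is a few tick-boxes and short edits to three sections, with no new procedure and no change to patient care. The remaining limit is a narrower claim: the scheduled checks come before surgery, and the removal item detects only visible blood, so symptomless injury without bleeding will still be missed.

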## **Methods and Measures**

### **Design**

Once the patient is recruited preoperatively in the PAC or within the hospital as an inpatient, this information will be relayed to the study investigators. On the day of surgery, the patient will then be randomized using a random number generator and opaque envelope method for group allocation to either extra-luminal placement of an EZ blocker bronchial blocker or left side double lumen tube. We will recruit at least 80 patients with right sided procedures: 40 EZ-Blocker and 40 left sided DLT. We will also recruit at least 80 patients with left sided procedures: 40 EZ-Blocker and 40 left sided DLT.

We will record age, height, weight, gender, ASA status, type of surgery, side of surgery, duration of one lung ventilation, duration of surgery, and duration of anesthesia.

An IV will be placed in the patient prior to going to the OR. Once in the OR the patient will have routine monitors placed. The patient will be pre-oxygenated with 100% O2 for 2 minutes and induced.. The patient will then be hand ventilated with 100% oxygen for 3 minutes to ensure relaxation. Patients will undergo direct laryngoscopy and according to group assignment will have either an extraluminal EZ-blocker placed or an appropriately sized left sided double lumen placed under the supervision of an attending experienced in thoracic anesthesia and one lung ventilation.

We will confirm endotracheal placement of the ETT or left sided DLT via auscultation and ETCO2. The ETT or DLT will be secured at an appropriated depth. The fiberscope will then be advanced into the lumen of the ETT or DLT to further adjust and confirm placement of the EZ-blocker or DLT. Time for initial bronchial blocker placement or DLT placement will be recorded from the point of the DL to removal of the fiberscope after visualization of the BB with the cuff inflated in the correct position or the DLT with the bronchial cuff inflated.

Other intravascular lines such as a radial arterial line and additional peripheral IV may be placed at the discretion of the attending anesthesiologist.

Once in the final position prior to prepping and draping the blocker or DLT in all groups will be checked to make sure it is still correctly placed with a FOB. The patient will be prepped and draped.

The surgeon will be blinded to technique and queried as to the quality of isolation upon entry into the chest and this will be recorded. This will be queried every 60 minutes for the duration of the procedure.

We will record any episodes of loss of isolation and details of repositioning including times and the issue of malposition i.e. the blocker or DLT slipped out or slipped in too far. We will record any episodes of ongoing desaturation which require deflation of the EZ-blocker cuff and/or ventilation of both lungs with a DLT.

We will record the point at which the surgeon the end of OLV. The patient will be extubated according to normal clinical practices and will be taken to the post anesthesia care unit. The Ez-blocker will be removed simultaneously with the ETT. In patients in the EZ-blocker group that remains intubated post procedure the EZ-blocker will be removed prior to going to the ICU. In the DLT group the DLT will be exchanged according to routine clinical practice to a single lumen ETT.

The patient will be contacted on post-operative days 1 and 2 to assessed for hoarseness and sore throat via a VAS scale from 0-100: 0=No sore throat and 100=the worst sore throat imaginable. We will also record any significant morbidity or mortality events such as prolonged mechanical ventilation or cardiac arrest or stroke that may occur within the first 2 post-operative days.

In patients where isolation is troublesome requiring multiple repositioning we will evaluate their preoperative CT scan to determine if there are any anatomical findings on CT which maybe predictive of failure. We will compare these to an equivalent number of control patients from this study population in which isolation was successful. We will attempt to match these patients for size and diagnosis.

The study will be performed at Wake Forest Baptist Medical Center a tertiary academic medical center.

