### **Analytical Plan**

Results will be analyzed initially using descriptive statistics. Comparison between groups will be done using chi square tests for proportions, and t-tests or ANOVA procedures for continuous variables. Other inferential statistical analysis will be conducted as appropriate.

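### Placement time ends only at a completed placement, so a patient whose allocated device cannot be placed has no valid time in the comparison

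*Combined protocol and SAP*

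**What the plan says.** Placement time is a secondary outcome. The Objectives section states: "An additional objective will be to assess time to placement of both devices". It appears again under Outcome Measure(s).

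The Design section defines the start of the interval: "Time for initial bronchial blocker placement or DLT placement will be recorded from the point of the DL". For the blocker, the interval ends at "removal of the fiberscope after visualization of the BB with the cuff inflated in the correct position". For the tube, the end point is "or the DLT with the bronchial cuff inflated"; correct position is not repeated there.

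The data sheet in Appendix 1 has a single device choice, "EZ-Blocker DOUBLE LUMEN", and a single line for the time, "Time for placement of EZ-blocker or DLT". It has no entry for allocated as against used device, for success or failure of the allocated device, or for an abandoned attempt. The replacement log on the same form concerns repositioning during the procedure. A failed first placement could be noted only in free text, under "Additional Comments/Adverse Events/Other significant intra-operative events".

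The Analytical Plan specifies "t-tests or ANOVA procedures for continuous variables". It names no analysis population and gives no rule for a patient without a completed placement.

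**The concern.** The stop event can occur only if placement succeeds. If the team cannot place the allocated device, or exchanges it during initial placement, the stop event for that device never happens. Two things can then reach the t-test. Either the time is left blank and the patient drops out, or the clock runs until the other device is in place and the entry mixes two devices.

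Missing times of this kind are informative, because the patients without a time are those in whom placement was hardest. A comparison of successes says how long placement takes when it works. The objective asks how the two devices compare in the patients randomised to them. If failure rates differ between arms, the difference in means is distorted, in a direction set by which device fails more often. The form does not reliably capture what would be needed to repair this afterwards.

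**Working it through.** **1. The plan's own figure.** The Sample Size section gives 36 per arm from repositioning rates of 0.5 and 0.3 per hour, SD 0.3, 80% power and 5% type 1 error. With a two-sided test, n = 2 × (1.960 + 0.842)² × 0.3² / 0.2² = 2 × 7.85 × 2.25 = 35.3, rounded up to 36. The figure reproduces and uses no placement-time input, so this point does not change it.

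**2. Inputs for placement time.** The protocol gives no mean, SD or failure rate for initial placement. All of the following are assumptions:
- mean time among successes: 5 min (EZ-blocker) and 4 min (DLT);
- time at which a failed attempt is abandoned: 15 min;
- failure proportions f_E (EZ-blocker) and f_D (DLT), varied below.

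**3. Formula.** Mean over all attempts in an arm = (1 − f) × success mean + f × 15. The success-only difference is 5 − 4 = 1.0 min whatever the failure rates. The difference over all attempts is

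(5 + 10 f_E) − (4 + 11 f_D) = 1 + 10 f_E − 11 f_D.

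**4. Results (minutes, EZ-blocker minus DLT).**

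| f_E vs f_D | EZ-blocker mean | DLT mean | Difference, all attempts | Success-only |
|---|---|---|---|---|
| 0% vs 0% | 5.00 | 4.00 | 1.00 | 1.0 |
| 2% vs 1% | 5.20 | 4.11 | 1.09 | 1.0 |
| 2% vs 2% | 5.20 | 4.22 | 0.98 | 1.0 |
| 5% vs 5% | 5.50 | 4.55 | 0.95 | 1.0 |
| 5% vs 2% | 5.50 | 4.22 | 1.28 | 1.0 |
| 10% vs 2% | 6.00 | 4.22 | 1.78 | 1.0 |
| 15% vs 5% | 6.50 | 4.55 | 1.95 | 1.0 |
| 2% vs 5% | 5.20 | 4.55 | 0.65 | 1.0 |

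Share of the all-attempts difference hidden by counting successes only:
- 5% vs 2%: 0.28 / 1.28 = 22%
- 10% vs 2%: 0.78 / 1.78 = 44%
- 15% vs 5%: 0.95 / 1.95 = 49%

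The last row of the table shows the opposite case: if the DLT failed more often, counting successes only would overstate the difference.

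**5. Patients involved.** With 80 patients per device (40 on each side), failure rates of 2%, 5%, 10% and 15% correspond to 1.6, 4, 8 and 12 patients in an arm.

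**The case against.** The strongest reply is that failed initial placement may be rare. Known or suspected difficult airways and BMI above 39 are excluded, both devices must be judged suitable, and an attending experienced in thoracic anesthesia supervises. The Background reports initial malposition as about equal for the two devices in an earlier trial. Malposition is not failed placement, but the report gives no support for a large imbalance. This stands: with rare or equal failures the effect is negligible, as the table shows.

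A second reply is that the consequence is inferred from silence: no sentence excludes failures, free text can record a switch, and the Analytical Plan allows other analyses as appropriate. That is fair as to what would actually be done. But neither free text nor a general allowance defines a time for a placement that never completed.

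Two stronger readings are tempting, and the documents support neither.
- **That the comparison flatters the EZ-blocker.** This needs the EZ-blocker to fail more often at initial placement, and no such rate is given. The Background does foresee outright failure with the EZ-blocker, but for right-sided isolation and as a trigger for the CT review.
- **That the randomised comparison is broken for every outcome.** This would follow only if the device tick recorded the device received and patients were analysed by it. The form does not say which device the tick means. The Design section has patients treated according to assignment and refers to groups by device, and nothing says the form is the only record of allocation.

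**Conclusion.** The point holds for placement time alone. As written, the end point is a completed placement, the form holds one device and one time, and the test compares means. A patient whose allocated device is not placed has no valid value. The two end points are also worded differently, since correct position is required in words only for the blocker.

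How much this matters cannot be determined from the protocol. On the assumed 5, 4 and 15 min, the effect ranges from nothing or almost nothing, when failures are absent, rare or equal, to about half of the difference hidden at 15% vs 5%. Its sign depends on which device fails more often. The change is worth making because it is cheap and the missing data may not be recoverable later. It does not bear on the main stability comparison.

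**What to change.** **Data form.** Replace the single device choice with two entries, allocated device and device in use at chest entry, and add a yes/no entry for whether the allocated device was placed successfully. The time at which an attempt was stopped may be recorded as an optional, descriptive item; the analysis below does not need it.

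**Definition.** Word the completed-placement end point in the same way for both devices.

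**Analysis.** State that patients stay in their allocated group; that placement time of the allocated device is compared by a rank test (for example Wilcoxon), with failed placements ranked worse than every observed time; and that the failure proportion is reported by arm beside it. Censoring failures at the time of abandonment would be a poor substitute, because the patients abandoned are those least likely to have succeeded.

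**Cost.** Two additional form entries, one relabelled entry and a sentence or two of analysis text. A rank summary is less direct than a difference in mean minutes. If no placement fails, little is lost. No rule on when to change device is proposed.

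### The blinded rating of lung isolation stops at the last full hour, so short cases have only the entry rating; one rating at the end of OLV would close the gap

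*Combined protocol and SAP*

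**What the plan says.** The Objectives section names two things to compare between the devices: how well each holds its position, and how well it isolates the lung.

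- **Who rates, and first when.** Design: "The surgeon will be blinded to technique and queried as to the quality of isolation upon entry into the chest and this will be recorded". No other assessor is stated to be blinded.
- **Later ratings.** Design: "This will be queried every 60 minutes for the duration of the procedure". The Outcome Measure(s) section repeats this as "quality of isolation at 1-hour intervals during the operation".
- **Form.** The Appendix 1 data form gives the scale as "Quality of Isolation: 1- Excellent 2 – Fair 3 - Poor" and defines the levels by the state of the lung. Its slots are T1, then "Time 60 min Quality of Isolation 60", and so on in steps of 60 up to 300 minutes. There is no slot for the end of OLV.
- **End of OLV.** Design: "We will record the point at which the surgeon the end of OLV" (a verb seems to have dropped out, but the sense is clear). The form also has a field for OLV time. No quality rating is tied to this point.
- **Separate log.** Design: "We will record any episodes of loss of isolation and details of repositioning including times and the issue of malposition". The form's event table has columns for time and for "Brief Description of event including duration of replacement event". The documents do not say who keeps this log or whether that person is blinded.
- **Case length.** The selection criteria admit thoracoscopic and open surgery and set no minimum duration.

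**The concern.** The background section argues that blockers may be less stable than double lumen tubes, particularly on the right side. Displacement develops during the case, so the ratings after entry carry most of the information on whether isolation lasts. Under the present schedule the number of such ratings depends on case length, and a short case has none: its only rating is taken before the device has been tested over time. In longer cases the last part of OLV is not rated.

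At stake is how much the blinded quality comparison can say about isolation after chest entry, and for how many patients. The Analytical Plan gives no rule for summarising ratings across cases of different length, so nothing there makes up for the uneven coverage.

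**Working it through.** **1. The plan's own figure.** The Sample Size section gives 0.3 repositionings per hour with the double lumen tube, 0.5 with the EZ-blocker (taken as per hour), SD 0.3, power 80% and type 1 error 5% (taken as two-sided).

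n = 2 × [SD × (z₀.₉₇₅ + z₀.₈₀) / difference]² = 2 × [0.3 × (1.960 + 0.842) / 0.2]² = 35.3, rounded up to 36 per arm.

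This reproduces the stated 36. The calculation uses the repositioning rate only; the plan gives no figure for the quality rating.

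**2. Coverage by the blinded rating.** Let L be the minutes from chest entry to the end of OLV, with queries at 0, 60, 120 and so on. Number of ratings = 1 + floor(L/60). Unrated tail = L − 60 × floor(L/60). The documents give no case lengths, so the values of L are illustrative.

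| L (min) | Ratings | Unrated tail (min) | Tail as share of L |
|---|---|---|---|
| 45 | 1 (entry) | 45 | 100% |
| 59 | 1 (entry) | 59 | 100% |
| 90 | 2 | 30 | 33% |
| 119 | 2 | 59 | 50% |
| 120 | 3 | 0 | 0% |
| 150 | 3 | 30 | 20% |

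**3. Events expected in the unrated time, at the plan's rates.** In a 30-minute tail: 0.3 × 0.5 = 0.15 repositionings per patient (double lumen tube) and 0.5 × 0.5 = 0.25 (EZ-blocker). In a case ending 59 minutes after entry, with Poisson events assumed, the chance of at least one is 1 − exp(−0.3 × 59/60) = 26% and 1 − exp(−0.5 × 59/60) = 39%. These events would be logged, but the only quality rating would be the one at entry.

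**4. Chance that a query falls within a loss.** Assume that the surgeon rates the moment and that a loss of d minutes starts at random. The documents give no value of d.

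| | d = 5 | d = 10 | d = 15 | d = 30 |
|---|---|---|---|---|
| Within a complete hour, d/60 | 8% | 17% | 25% | 50% |
| Whole of a 90-minute OLV, d/90 | 6% | 11% | 17% | 33% |
| Whole of a 150-minute OLV, 2d/150 | 7% | 13% | 20% | 40% |

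For a 45-minute OLV it is 0% at any d. Within a complete hour, a 45-minute loss is caught 75% of the time.

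**5. Does sparse sampling bias the comparison?** If losses are unrelated to the query clock, the expected share of poor ratings equals the share of covered time spent in that state. A device with twice the lost time should show twice the share of poor ratings. Fewer queries widen the uncertainty, and the tail is not sampled; neither by itself pulls the contrast toward zero.

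**6. What one rating at the end of OLV adds.** With d = 10, the chance of catching a loss goes from 0 to 10/45 = 22% at 45 minutes of OLV, from 11% to 2 × 10/90 = 22% at 90, and from 13% to 3 × 10/150 = 20% at 150. The main gain is that no patient is left with the entry rating alone.

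**The case against.** The strongest reply is that the trial does not lose these events. Design requires every loss of isolation and every repositioning to be recorded with times, and the form has a replacement count and an event table. Displacement is thus followed throughout, including in short cases and after the last full hour, and it is the endpoint on which the trial was sized. A rating sampled in time together with an event count is a coherent pair. The form's slots run to 300 minutes, so long cases were foreseen, and no section shows how common short ones are. All of this stands.

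It does not fill the gap in the quality outcome. The event table has no 1-to-3 field, so a slip from excellent to fair that prompts no repositioning has no place there. Nothing states that whoever keeps the log is blinded; equally, nothing states that this person is not.

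A reader might go further and infer that hourly ratings miss most losses and so favour a finding of no difference. The documents do not support that. The share missed depends on how long losses and OLV last, and neither is given. Step 5 shows that fixed-time ratings are not inherently biased for the time they cover. That the surgeon rates the moment, and not the past hour, is itself an inference from the timed slots.

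**Conclusion.** The point holds as a gap in coverage and precision. On the present schedule a case ending less than 60 minutes after chest entry has one blinded quality rating, taken at entry. A longer case can have up to 59 minutes at its end without one. This follows from the schedule alone, with the 60-minute clock taken to start at chest entry. How many patients it affects cannot be computed, because the documents give no case durations.

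The repositioning endpoint and the 36 per arm (40 enrolled per device and side) are untouched. A bias toward no difference is not shown, and the percentages in step 4 illustrate assumptions and are not estimates for this trial. The point ranks as a cheap improvement to an outcome that was not sized.

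**What to change.** Keep all existing ratings. Add one query to the same surgeon when OLV ends, a time already recorded, on the same 1-to-3 scale. Amend the Design and Outcome Measure(s) sections accordingly, and add an end-of-OLV row to the data form. Every patient then has at least one rating after entry that can be compared by device, whatever the case length.

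A question on the worst isolation since the previous query may be added, but only as a secondary descriptive item. It relies on up to 60 minutes of surgeon recall, may be coloured by knowing that the device was repositioned, and its worst value over the case tends to worsen as OLV lengthens. It would also partly repeat the repositioning count.

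The core change costs one spoken question per case and one form row. The sample size does not change.
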